8.1.4 Adverse events outcome

Outcome is classified as follows:

1. Recovered – The subject has fully recovered from the AE with no residual effects observable.
2. Recovered with sequelae – The subject has fully recovered from the AE with residual effects.
3. Ongoing – AE is still ongoing by the end of study.
4. Unknown.
5. Death.

8.1.5 Causality Assessment of Adverse events

All AEs will be evaluated by the investigator and assigned an estimated relationship to the investigational product. As empagliflozin safety profile is well established, the investigator should consider it when evaluating AE relationship to empagliflozin. The terms "probable", "possible", "remote", or "unrelated" refer to the association with the use of the investigational product, as defined below.

Medical judgment should be used to determine the relationship, considering all relevant factors, including pattern of reaction, temporal relationship, de-challenge or re-challenge, confounding factors such as concomitant medication, concomitant diseases and relevant history.

Assessment of causal relationship should be recorded directly in participant CRF.

AEs associated with the use of investigational product

AEs associated with the use of investigational product (i.e. probably or possibly related to treatment as defined below) are also termed Adverse Drug Reactions (ADRs).

Probable: AE that are considered with a high degree of certainty to be related to the investigational drug. An AE is considered probably related if:

- It follows a reasonable temporal sequence to the administration of the drug.
- It cannot be reasonably explained by the known characteristics of the patient subject's clinical state, environmental factors, or other modes of therapy administered to the subject.
- It follows a known pattern of response to the drug.

Possible: AE in which the connection between the investigational drugs appears unlikely but cannot be ruled out with certainty. An AE may be considered possibly related if:

- It follows a reasonable temporal sequence to the administration of the drug.
- It may have been produced by the patient's clinical state, environmental factors, or other modes of therapy administered to the patient.
- It follows a known pattern of response to the drug.

AEs not associated with the use of investigational product

Remote: AE that meet the following criteria:

- It does not follow a reasonable temporal sequence to the administration of the drug.
- It may readily have been produced by the subject's clinical state, environmental factors, or other modes of therapy administered to the subject.
- It does not follow a known pattern of response to the drug.

Unrelated: AE that are judged to be clearly and incontrovertibly due only to extraneous causes, and do not meet the criteria for Probable, Possible, or Remote defined above.

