4.6 Premature whole study termination

- Administrative problems e.g.: recurrent serious or severe ADR clinically evaluated by PI and/or sponsor as warranting whole study termination.
- A decision made by the sponsor and/or IRB/EC and/or local regulatory agency to terminate the study

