8.1.1 Definitions of adverse events

Adverse event

An adverse event is defined as any untoward medical occurrence or effect in a patient treated on a study protocol, which does not necessarily have a causal relationship with the study treatment. An AE is therefore described as any unfavorable and unintended sign (including an abnormal laboratory finding), symptom or disease temporally associated with the use of the study treatment, whether or not considered related to the study treatment. This definition includes any abnormalities or anomalies that were not seen at baseline or which worsened during the course of the study, if present at baseline.

Adverse Reaction (AR)

This is defined as **all untoward and unintended responses to a study treatment related to any dose administered**. A causal relationship between the study treatment and an AE is at least a reasonable possibility (probably or possibly related), i.e. the relationship cannot be ruled out.

Serious Adverse Event

A serious AE (SAE) is defined as any AE occurring at any dose that results in any of the following outcomes:

- death
- a life-threatening AE, as defined below
- patient hospitalization or prolongation of existing hospitalization
- a persistent or significant disability/incapacity

- a congenital anomaly/birth defect
- important medical event, as defined below

A life-threatening AE is any AE that places the subject, in the view of the investigator, at immediate risk of death from the reaction as it occurred (i.e. it does not include a reaction that, had it occurred in a more severe form, might have caused death).

An important medical event is an AE that may not result in death, be life-threatening, or require hospitalization but may be considered a serious AE when, based upon appropriate medical judgment, may jeopardize the subject and may require medical or surgical intervention to prevent one of the outcomes listed above. It can also include AEs otherwise judged to be serious by either the investigator or the sponsor.

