Investigators should note that not all criteria in the table below need to apply for the diagnosis of DKA, and clinical judgment should also be taken into consideration. Due to its mechanism of action, empagliflozin may potentially modify the clinical presentation of DKA which may occur at lower plasma glucose levels than stated in the table below.

Table 3 Diagnostic criteria for DKA

Table 3 Diagnostic criteria for DKA

	DKA		
	Mild	Moderate	Severe

Plasma glucose (mg/dL)	>250	>250	>250
Arterial pH	7.25-7.30	7.00-7.24	<7.00
Serum bicarbonate (mEq/L)	15-18	10 to <15	<10
Urine ketones*	Positive	Positive	Positive
Serum ketones*	Positive	Positive	Positive
Effective serum osmolality (mOsm/kg)**	Variable	Variable	Variable
Anion gap***	>10	>12	>12
Alteration in sensoria or mental obtundation	Alert	Alert/drowsy	Stupor/coma

* Nitroprusside reaction method

** Calculation: $2[\text{measured Na (mEq/L)} + \text{gluc}]$

Contact details of the local pharmacovigilance unit/LVPM: E-mail: PV_local

[contact]

Suspected Unexpected Serious Adverse Reaction (SUSAR) This is defined as an adverse reaction, the nature or severity of which is not consistent with the known study treatment information.

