8.2.3 Expedited Reporting

Expedited reporting by PI to IRB/EC is warranted for all Suspected Unexpected Serious Adverse Reactions (SUSAR), i.e. unexpected SAEs that are considered related to study product as defined in [Section 8.1.5](#). Additional cases will be communicated by PI to IRB/EC via expedited reporting when required by local regulation.

Any SAE, irrespective of causality, occurring in a patient after providing informed consent and until four weeks after ending study participation / study drug administration must be reported. SAEs occurring afterwards should only be reported if considered by the investigator attributable to the sponsor investigational drug(s).

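### Section 8.1.5 lists a known pattern of response under both related categories; read literally, this leaves a new kind of reaction unclassified and conflicts with the protocol's adverse-reaction and SUSAR definitions

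*Combined protocol and SAP*

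**What the plan says.** Section 8.1.5 has four causality categories. Probable and Possible together make up the adverse drug reactions; Remote and Unrelated are the events not associated with study drug.

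- **Probable** opens with "An AE is considered probably related if" and lists reasonable timing, no other reasonable explanation, and "It follows a known pattern of response to the drug".
- **Possible** is defined as an "AE in which the connection between the investigational drugs appears unlikely but cannot be ruled out with certainty". Its list opens with "An AE may be considered possibly related if" and has the same first and third bullets. Only the second differs: another cause may have produced the event.
- **Remote** covers events that meet three criteria: timing not reasonable, another ready cause, and no known pattern.
- **Unrelated** is for events beyond doubt due to outside causes alone that do not meet the criteria for the other three.

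The same section asks for medical judgment across all relevant factors, with pattern of reaction named as one of them. It also tells the investigator to consider the drug's established safety profile.

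Elsewhere, section 8.1.1 defines an adverse reaction with the sentence "A causal relationship between the study treatment and an AE is at least a reasonable possibility". It equates this both with probably or possibly related and with a relationship that cannot be excluded. At the end of section 8.1.2 a SUSAR is an "adverse reaction, the nature or severity of which is not consistent with the known study treatment information". Section 8.2.3 sends to the IRB/EC, by expedited report, "unexpected SAEs that are considered related to study product as defined in" section 8.1.5. Section 8.2.3.1, on sponsor reports to the PI, takes relatedness from section 8.1.1 instead.

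**The concern.** Causality and expectedness are separate questions. A SUSAR has to be related and unexpected, and it may be unexpected in nature or in severity. If being related requires a known pattern, a reaction of a new nature meets the second half of the definition by failing the first.

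The classification has consequences. It decides expedited reporting under 8.2.3 and which events enter the study-drug-related summary in 9.2.2. It also bears on the example given in 4.6 for ending the whole study, "recurrent serious or severe ADR clinically evaluated by PI", and on the grade 3/4 adverse drug reaction reason in 4.4.1.

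The population makes an unfamiliar reaction a fair thing to plan for: device-implanted heart-failure patients at high arrhythmic risk, in a trial looking for a new cardiac effect. The instruction to consider the established safety profile pushes the investigator further towards known effects.

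**Working it through.** No figure is at issue, so the check sets the passages side by side.

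**Step 1. Are the bullets criteria?** Neither the Probable nor the Possible list says whether all bullets or any one is needed. Two features point to all:

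- The Unrelated definition refers to the criteria for the other three categories.
- Timing and pattern are worded identically under Probable and Possible. If any one bullet sufficed, plausible timing alone would make an event both Probable and Possible, and the lists would not separate the two.

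**Step 2. Apply the lists with every bullet required.** Cross timing (2) × known pattern (2) × other cause (2) = 8 combinations.

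| Timing | Known pattern | Other cause | List met in full |
|---|---|---|---|
| plausible | yes | no | Probable |
| plausible | yes | yes | Possible |
| plausible | no | no | none |
| plausible | no | yes | none |
| not plausible | yes | no | none |
| not plausible | yes | yes | none |
| not plausible | no | no | none |
| not plausible | no | yes | Remote |

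Three combinations meet a list and 8 − 3 = 5 do not. The two that matter here are plausible timing without a known pattern:

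- Both fail Probable and Possible on the pattern bullet.
- Both fail Remote on timing, so the presence of another cause does not rescue them.
- With no other cause, the event cannot be Unrelated. With another cause, it is Unrelated only if that cause is beyond doubt the sole one.
- The strongest new signal (plausible timing, no other cause) fails Possible twice: on pattern, and on the bullet that expects another possible cause.

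Such an event is left unclassified. It is not defined as unrelated.

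**Step 3. Follow the chain to a SUSAR.** Section 8.2.3 needs relatedness under 8.1.5. On the literal reading an event of a new nature does not have it, although the definition in 8.1.2 expressly includes reactions unexpected in nature. An event of known type but unexpected severity can qualify on either reading.

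**Step 4. Look for a cure elsewhere.** The 8.1.1 test would admit the event, but it is equated with probably or possibly related, which leads back to the 8.1.5 lists. The differing references in 8.2.3 and 8.2.3.1 mean that two SUSAR routes rest on two definitions. Section 8.2.2 does ask for listedness and the investigator's causal assessment as separate items, so the separation of the two questions exists in the protocol but is not carried into 8.1.5.

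**The case against.** A reader might infer that a reaction of a new kind can never be called related and so never becomes a SUSAR. The documents do not support that. Neither related list states that every bullet is required. Possible is worded permissively and defined by a link that cannot be excluded, and medical judgment over all factors is required. An investigator who treats the bullets as factors to weigh can rate the event Possible, and it can then be a SUSAR. The five empty combinations also suggest that the lists were meant as guidance and not as a closed algorithm.

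A reader might also infer that the event disappears from safety oversight. It does not:

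- Under 8.2.2, SAEs and AESIs go to the sponsor whatever their relationship to study drug, with an initial SAE report within 24 hours, and the PI submits SAE reports to the IRB/EC under local regulations.
- Section 8.2.3 repeats that SAEs are reported irrespective of causality and allows further expedited reports where local regulation requires them.
- Sections 4.4.1, 4.5 and 4.6 each contain stopping routes that need no adverse-drug-reaction label.
- Worsening ventricular arrhythmia is a poor example of a hidden harm: NSVT, sustained VT, VF, ATP and shocks are device-captured endpoints (4.1.2, 7.2, 7.3) summarised by treatment (9.2.1).

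All of this stands, and it limits the consequences. It does not remove the conflict. Two investigators could rate the same event differently and each cite 8.1.5. That section assigns causality to the investigator, and the protocol describes no sponsor override of that call.

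**Conclusion.** The point holds as a conflict between stated rules. Read literally as criteria, 8.1.5 gives no category to an event with plausible timing and no known pattern, in both such combinations out of eight, apart from the narrow Unrelated exit. That contradicts the 8.1.1 test, the SUSAR definition and the judgment wording within 8.1.5 itself.

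Three things are at risk: classification as related, expedited SUSAR reporting under 8.2.3, and the completeness of the study-drug-related summary in 9.2.2. Receipt of SAEs by the sponsor, and the ability to stop treatment or the study, do not depend on it.

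The conclusion rests on reading the bullets as jointly required. That is the more natural reading but is not stated. If they are factors to weigh, the conflict becomes an ambiguity that can still produce inconsistent ratings. How many events would be affected cannot be estimated from the documents.

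**What to change.** - In 8.1.5, make known pattern a supporting feature for Probable and Possible, not a condition, and say whether the remaining bullets are all required or are to be weighed.
- Define Possible by the 8.1.1 test: a reasonable possibility, with the relationship not excluded.
- State that expectedness is judged separately, against the drug reference information already named in 8.2.2, and plays no part in causality.
- Make 8.2.3 and 8.2.3.1 refer to the same definition of relatedness.

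Without the pattern condition, plausible timing leads to Probable when there is no other cause and to Possible when there is one, so both empty combinations at issue are filled. The other three all have implausible timing and would be decided by the test in 8.1.1.

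The cost is an amendment to the wording of these sections and to any matching CRF instructions. The downside is that somewhat more events will be classed as related and expedited. No visit, assessment or efficacy analysis changes.

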8.2 Adverse events reporting and monitoring requirements

8.2.1 General

All adverse events, serious and non-serious, will be fully documented in both source documents and CRF, and each AE will be assessed in light of its clinical significance. For each adverse event, the investigator will provide the onset, end, intensity, treatment required, outcome, seriousness and action taken with the investigational drug. The investigator will determine the relationship to the investigational drug, i.e. causality assessment, for each AE.

Events occurring prior to initiation of first dose should be recorded on the Medical History page of the CRF. Any AE occurring after initiation of the first dose and/or during any point throughout the study should be recorded on the Adverse Event page of the CRF. All adverse events occurring up to 30 days after the last dose of study drug administration should be captured in the CRF. AEs should be recorded in the CRF using the CTC AE terminology (short name). Whenever possible, diagnoses should be given when signs and symptoms are due to a common etiology.

Occurrence of any grade 4 AE must warrant clinical evaluation by the treating investigator to decide whether it is considered an SAE. If it is an SAE the investigator should report it to the sponsor within 24 hours (see [section 8.2.2 SAE Reporting](#)). Grade 4 AEs, which were not considered SAEs by the investigator, should be reviewed by the monitor who will forward them to the sponsor's medical monitor to approve that none of the AEs are SAEs.

A complete SAE report (i.e. With no missing information) must be sent to the sponsor at the first possible date and no later than 7 calendar days after SAE end date.

SAE will be recorded on designated CRF forms in a timely manner and no later than 7 calendar days after its end date.

Where a SAE is followed by reports of recurrent episodes, re-exposure, complications or progression of the initial SAE, all such reports must be reported as follow-up to the original episode. If a new SAE occurring at a different time interval is considered completely non-associated to a previously reported one, a new SAE form should be submitted as an initial report.

The PI or his designee will submit the SAE report to IRB/EC according to applicable local regulations.

8.2.3 Expedited Reporting

Expedited reporting by PI to IRB/EC is warranted for all Suspected Unexpected Serious Adverse Reactions (SUSAR), i.e. unexpected SAEs that are considered related to study product as defined in [Section 8.1.5](#). Additional cases will be communicated by PI to IRB/EC via expedited reporting when required by local regulation.

Any SAE, irrespective of causality, occurring in a patient after providing informed consent and until four weeks after ending study participation / study drug administration must be reported. SAEs occurring afterwards should only be reported if considered by the investigator attributable to the sponsor investigational drug(s).

8.2.3.1 Sponsor Reporting SUSARs to PI

The sponsor should report all Suspected Unexpected Serious Adverse Reactions (SUSARs), i.e. unexpected SAEs that are considered related to study product as defined in [Section 8.1.1](#), to the PI in the following timelines: death and other life threatening events will be reported within 7 days of the date the event was reported to sponsor and the rest of the SUSARs will be reported to the PI within 15 days. The sponsor should provide the PI with the list of SUSARs that occurred in all of the sites periodically, at least once every 6 months. The report will include a summary of the main safety issues of the study product that came up during the reporting period.

8.2.3.2 Reporting SUSAR to the Israeli MOH

The sponsor should report SUSARs to the Israeli MOH in an annual Development Safety Update Report (DSUR), which describes all of the new safety information accumulated during the year. The report should include a summary and conclusions of the main safety issues of the study product.

The DSUR should be sent to [contact] within 60 days of the data lock. In addition, the sponsor should send the MOH the DSUR on a CD with an accompanying letter. The sponsor should inform the PI and the MOH of the following information within 7 days of receiving it:

- a. Decisions of regulatory authorities regarding the continuation of the study
- b. Any decision to discontinue the study for any reason, temporarily or permanently.

All notifications to the MOH should be sent to:

[contact]

Any pregnancy of a study subject or a partner of a male subject after the first dosing is considered an immediately reportable event.

Such events must be reported within one (1) working day of the investigator becoming aware of the event. Pregnancies shall be followed for the duration of the pregnancy. It is the PI's responsibility to provide to the sponsor follow-up

information on the outcome of the pregnancy including information about any sequelae.

Information about all serious adverse events will be collected and recorded on the Serious Adverse Event Report Form.

Additional safety examinations and procedures

If any unclear clinical event, including symptoms, signs, or other observations or abnormalities, should occur, the Investigator, or any other physician in charge, may perform additional clinical examinations and procedures (other than outlined in this protocol), including any clinical, laboratory, imaging and/or technical testing, in order to clarify and establish the etiology and diagnosis of this clinical event.

8.3 Pregnancies

Any pregnancy of patient or patient's spouse that occurs during study participation should be reported using a Clinical Trial Pregnancy Form. To ensure patient safety each pregnancy must also be reported to the sponsor and BI within 24 hours of learning of its occurrence. The pregnancy should be followed up to determine outcome, including spontaneous or voluntary termination, details of birth, and the presence or absence of any birth defects or congenital abnormalities or maternal and newborn complications.

8.4 Laboratory evaluations

Laboratory results will be reported to the investigator who will review abnormal laboratory findings for clinical significance. The investigator will document any laboratory test results that are clinically significant on the lab report and provide details of the relationship to investigational product and the action taken. If a change in a laboratory value represents a medical condition, the medical condition will be listed in the AE record unless this is a pre-existing medical condition allowed under the inclusion criteria. If no correlation is possible, the direction of change (increase or decrease) and the actual value will be recorded.

The institution will perform laboratory analyses according to the Visit Schedule (see [Table 2](#)). The sponsor must be provided with a copy of the laboratory's certification, and a tabulation of the normal ranges for each parameter required. Additionally, if at any time a patient has laboratory parameters obtained from a different outside laboratory, the sponsor must be provided with a copy of the certification and a tabulation of the normal ranges for that laboratory.

At any time during the study, abnormal laboratory parameters which are clinically relevant (e.g. require dose modification and/or interruption of study drug, lead to clinical symptoms or signs or require therapeutic intervention), whether specifically requested in the protocol or not, must be recorded on the appropriate Comment CRF page in addition to the appropriate laboratory CRF page. When abnormal laboratory values or test results constitute an adverse event (i.e., induces clinical signs/symptoms or requires therapy) they must be recorded on the Adverse Events CRF.

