2.5 Clinical data to date

Adverse reactions excluding hypoglycemia reported in $\geq 2\%$ of patients treated with empagliflozin and greater than placebo in pooled placebo-controlled

clinical studies of empagliflozin monotherapy or combination therapy reflecting exposure of 1976 patients to empagliflozin:

Table 1

	Number (%) of patients		
	Placebo N=995	Empagliflozin 10 mg N=999	Empagliflozin 25 mg N=977
Urinary tract infection	7.6%	9.3%	7.6%
Female genital mycosis	1.5%	5.4%	6.4%
Upper respiratory tract infection	3.8%	3.1%	4.0%
Increased urination	1.0%	3.4%	3.2%
Dyslipidemia	3.4%	3.9%	2.9%
Arthralgia	2.2%	2.4%	2.3%
Male genital mycotic infections	0.4%	3.1%	1.6%
nausea	1.4%	2.3%	1.1%

Other adverse events observed in clinical studies: thirst was reported in 1.5% to 1.7% of patients treated by empagliflozin, most probably secondary to volume depletion due to osmotic diuresis properties of empagliflozin. Volume depletion caused by osmotic diuresis is the cause of: arterial hypotension, dehydration and orthostatic hypotension that were reported in 0.3% to 0.5% in clinical trials with empagliflozin.

Mild impairment in renal function (increased serum creatinine or decrease in GFR) especially in persons with preexisting moderate renal impairment was noticed in clinical trials involving empagliflozin.

Dose related increase in LDL cholesterol was observed in 4.6% to 6.5% versus 2.3% in the placebo group.

Hypoglycemia was observed in clinical trials when empagliflozin (10mg) was administrated as monotherapy in 0.4% of patients. Combination therapy with metformin resulted in hypoglycemia rate of 1.8% (versus 0.5% with placebo and metformin). Combination therapy with insulin resulted in hypoglycemia rate of

19.5% (versus 20.6% with placebo and insulin). Combination therapy with metformin and sulfonylurea resulted in hypoglycemia rate of 16.1% (versus 8.4% with placebo and the baseline drugs).

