8.1 Adverse events

The information obtained during study visit subject questioning, review of subject's compliance record, physical examinations, vital signs measurements, blood testing, and by any other means will be evaluated in light of baseline medical data and thus provide the basis for adverse events identification and grading. The adverse events reported during the trial will be graded (see [8.1.3 below](#)), documented and assessed in light of their clinical significance and relation to investigational product. In addition, the following information regarding the AE must be obtained: start date, end date (if applicable), outcome (resolved / unresolved), and action taken (e.g. dose adjustment, therapy discontinuation, concomitant medication). Adverse event monitoring will be conducted throughout subject's participation.

Information about all adverse events, whether volunteered by the patient, discovered by investigator questioning, or detected through physical examination, laboratory test or other means, will be collected and recorded on the Adverse Event Case Report Form and followed as appropriate.

Medical conditions/diseases present before starting study treatment are only considered adverse events if they worsen after starting study treatment.

Clinical events occurring before starting study treatment but after signing the informed consent form are recorded on the Medical History/Current Medical Conditions Case Report Form. Abnormal laboratory values or test results constitute adverse events only if they induce clinical signs or symptoms leading to a premature control of the abnormal value before the next scheduled laboratory test, leading to a change in study medication (e.g. dose

modification, interruption or permanent discontinuation), requires a change in concomitant therapy (e.g. addition or change in a concomitant medication, therapy or treatment) or require therapy.

Any Adverse Event occurring by the time of study completion (within four weeks of last drug intake) must be recorded on the Adverse Event CRF page.

Any adverse event term needs to be provided for each event; preferably using the short name based on the CTCAE ver. 4.0 or preferred term on the MedDRA.

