Appendix 1 Diabetes medication titration

Researches will make an effort to prevent hypoglycemia events and worsening hyperglycemia at all stages of the study. All patients will receive an endocrinology consultation on diabetes medication titration prior to starting any study medication. Any changes in the diabetes treatment regimen are allowed apart from initiating SGLT2 inhibitors.

The consultation will include instruction to monitor fasting glucose closely on the first week of each period of the study, to make changes in medication doses upon initiation of each study period (including a specific recommendation for the washout period) and in any case that glucose is over 150 for 3 consecutive days (see details on specific medication below). This instruction will be repeated by the cardiologist on subsequent visits at the beginning of washout and at the beginning of the second treatment period. If at any point of the study fasting glucose is over 180 for 7 days despite taking the following measures – schedule emergency endocrinology consultation within a week.

Decision to titrate depends on patient glycemic control prior to study:

- A. Patients with HbA1c over 7.5% and fasting glucose usually over 150 with no hypoglycemia events or glucose measurements under 90 – no change in diabetes medications or insulin.

- B. Patients with fasting glucose usually under 150 or HbA1c under 7.5% - when oral medication (empagliflozin or placebo) is started reduce insulin by 20%, stop sulfonylurea and repaglinide, titrate as indicated below according to glucose measurements.

Basal insulin

If fasting glucose usually under 150 or HbA1c under 7.5% - reduce by 20% upon initiation of study medication. Otherwise no change.

Further titration by the patient throughout study:

If fasting glucose for 3 days is: Basal insulin should be changed by:

- >180 mg/dL → increase by 4 units
- >140 mg/dL → increase by 2 units
- <110 mg/dL → decrease by 2 units
- <100mg/dL → decrease by 4 units

If fasting glucose in even one measurement is low, reduce basal insulin:

- <90mg/dL → decrease by 4 units
- < 80 mg/dL → decrease by 6 units

Prandial insulin or insulin mixes

If preprandial noon/evening/bedtime glucose is under 100 - decrease all doses by 20%

If noon+evening+bedtime glucose is over 150 for 3 days – increase dose by 10%

Sulfonylurea

If fasting glucose under 150 mg/dL or HbA1c under 7.5% - stop

Then:

If fasting glucose over 150 for 7 days restart at half dose

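### Section 8.4 keeps laboratory changes in entry conditions off the AE record without excepting worsening, which contradicts 8.1, 8.1.1 and its own last sentence; type 2 diabetes is the condition mainly exposed

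*Combined protocol and SAP*

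**What the plan says.** Four statements in the protocol bear on whether a laboratory change in a patient's entry condition is an adverse event.

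- **8.4, the exemption.** A change in a laboratory value may represent a medical condition. If so, "the medical condition will be listed in the AE record unless this is a pre-existing medical condition allowed under the inclusion criteria".
- **8.4, the last sentence.** "When abnormal laboratory values or test results constitute an adverse event (i.e., induces clinical signs/symptoms or requires therapy) they must be recorded" on the AE form. It makes no exception for pre-existing conditions. The sentence before it sends other clinically relevant values, including those that interrupt study drug, to the Comment and laboratory CRF pages.
- **8.1.** "Medical conditions/diseases present before starting study treatment are only considered adverse events if they worsen after starting study treatment". The same section has a separate rule for laboratory results: "Abnormal laboratory values or test results constitute adverse events only if they induce clinical signs or symptoms" or have one of several further listed consequences. These are early control of the value, a change in study medication, a change in concomitant therapy, or a need for therapy.
- **8.1.1.** The AE definition names abnormal laboratory findings and covers "any abnormalities or anomalies that were not seen at baseline or which worsened during the course of the study, if present at baseline".

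The inclusion criteria (5.1) require heart failure with reduced ejection fraction (criterion 1) and type 2 diabetes (criterion 4). Renal function is not among them; it appears only as an eGFR limit in the exclusion criteria (5.2).

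**The concern.** The exemption is triggered by a change in a value. It therefore reaches worsening as well as a stable abnormal result, and it applies to the conditions that every patient has on entry. An investigator who follows 8.4 and one who follows 8.1 can record the same event differently.

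For diabetes the effect need not be even across treatments. Section 2.2 says empagliflozin lowers glucose. Appendix 1 reduces insulin and stops sulfonylurea and repaglinide in the better-controlled patients when either study medication is started. Laboratory-detected glycaemic worsening is therefore plausibly likelier on placebo, and inconsistent recording could bias the AE comparison by treatment.

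A planned table could also be affected. Section 9.2.2 summarises AEs leading to discontinuation separately, and 4.4.1 lists a study-drug interruption of more than 14 consecutive days as a reason for discontinuation. A worsening that only interrupts study drug could end in discontinuation without an AE behind it.

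**Working it through.** No arithmetic applies, because the plan gives no figure for these events. The check sets the rules side by side for one case: type 2 diabetes present at entry, with a laboratory result after the first dose that shows worsening.

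| What the worsening leads to | 8.1, laboratory rule | 8.4, exemption | 8.4, last sentence |
|---|---|---|---|
| Symptoms, or therapy needed | AE | Not listed | AE form |
| Only an early repeat test or a study-drug change | AE | Not listed | Not on its list |
| Nothing | Not an AE | Not listed | Not an AE |

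**Row 1.** Section 8.4 contradicts itself. The exemption keeps the condition off the AE record and the last sentence requires it on the AE form. Sections 8.1 and 8.1.1 agree with the last sentence.

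**Row 2.** Section 8.1 makes this an AE, but neither sentence of 8.4 captures it. At most it reaches the Comment and laboratory pages. This row takes 8.1's consequences as alternatives. The wording there is loose: early control and study-drug change could be read as counting only when they follow symptoms. On that narrower reading 8.1's laboratory rule no longer covers row 2, although 8.1's sentence on pre-existing conditions and the definition in 8.1.1 still would. Row 1 is unaffected.

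**Row 3.** The exemption changes nothing against 8.1's laboratory rule. The definition in 8.1.1 is broader and would include any worsening, so 8.1 and 8.1.1 are not fully aligned either.

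The other conditions, by the same reading:

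- **Heart failure** is an inclusion condition, but the exemption concerns laboratory changes only. The chemistry panel in 8.4.2 contains no heart-failure marker, and NT-Pro-BNP is a secondary endpoint summarised by treatment (9.2.1). Clinical worsening is an AE under 8.1 and does not pass through this rule.
- **Renal impairment** is not named in the inclusion criteria, so it is not exempt on the literal wording.

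The timing of the reference values matters for the fix. In Table 2, safety bloods are scheduled at visits 1, 2, 3 and 5, and HbA1c at visits 1, 3 and 5. The last value before the first dose is therefore at visit 2 for chemistry and at visit 1 for HbA1c.

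**The case against.** The strongest reply is that little is lost. The last sentence of 8.4 recovers symptomatic or treated worsening, and 8.2.1 asks for any AE after the first dose to be recorded. Section 8.1 already leaves out laboratory drift without consequences. Clinically relevant results go on the Comment and laboratory pages, laboratory data are graded by CTCAE (9.2.2), and ketoacidosis is an adverse event of special interest (8.1.2). Much glucose management under Appendix 1 also runs on home readings, which are not the laboratory results that 8.4 addresses.

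Most of this stands, and it limits the size of the point. It does not remove the conflict: for treated worsening the reader of 8.4 still has two opposite instructions. Laboratory grading also does not put an event into the AE tables by system organ class and preferred term.

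Three stronger readings are tempting, and the documents do not support them.

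- **Creatinine rises are exempt too, so the distortion runs in both directions.** Section 2.5 reports renal effects of empagliflozin "especially in persons with preexisting moderate renal impairment". By the MDRD formula in 5.2, a 65-year-old man with eGFR 50 has a creatinine of about 1.42 mg/dL. A 50% rise to 2.13 gives eGFR 50 × 1.5^(−1.154) = 31.3, and the rise is below the 2-fold threshold for an event of special interest. The arithmetic is right, but renal impairment is not an inclusion condition, so the exemption does not reach it unless a site loosely reads inclusion criteria as eligibility. The argument for distortion towards empagliflozin rests on creatinine alone and falls with it.
- **Worsening heart failure drops out of the AE tables.** It does not, for the reasons given in the check above.
- **A count of lost events can be derived from the 128 patients.** An assumed rate of 10% to 30% would give 128 × 0.10 = 12.8 to 128 × 0.30 = 38.4 patients. The rate has no source in the documents, and the product ignores both 8.1's list of consequences and the last sentence of 8.4. That all 128 have diabetes says how many patients the clause can apply to, not how many events it removes.

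**Conclusion.** Wrong as written, minor. The exemption in 8.4 conflicts with 8.1, with 8.1.1 and with the last sentence of 8.4, and the practical exposure is laboratory-detected worsening of type 2 diabetes. Treated worsening is open to inconsistent recording. Worsening that leads only to an early repeat test or a study-drug change is an AE under 8.1 but not under 8.4, if 8.1's consequences are read as alternatives. That such worsening is likelier on placebo is an inference from the drug's glucose-lowering effect and the initial medication cuts in Appendix 1, not a figure in the plan. The effect on the AE tables cannot be sized from the documents.

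**What to change.** Three wording changes in the protocol, repeated in the CRF completion guide:

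1. In 8.4, replace the exemption with: *unless this is a condition present before the first dose that has not worsened from its last pre-dose value (visit 2 for chemistry, visit 1 for HbA1c)*.
2. State in 8.4 that 8.1 and 8.1.1 govern what is an adverse event.
3. Align the last sentence of 8.4 with the full list in 8.1, set out as separate items: symptoms, early control of the value, change in study medication, change in concomitant therapy, need for therapy. Say that laboratory drift without any of these is not an AE, so that the change does not bring in trivial fluctuation.

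The cost is a short amendment and slightly higher AE counts. No visit, test or analysis changes.
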